Research Study Protocol

Cover-Page

Study Title: Home-Based Dual-Task Training for Older Adults Date of Document: 02/07/2024 NCT#: NCT05108246

Study Protocol Title

Home-Based Dual Task Exercise for Older Adults

Investigative Team and Study Site

Principal Investigator: [name]

Co-Investigator: [name] MD

Study site

University at Buffalo, SUNY Jacobs School of Medicine and Biomedical Sciences

Research Synopsis

Title: Home-based Dual-Task Exercise for Older Adults

Clinical Phase: II

Study Population: Community-Dwelling adults, 65 years or older

Study Design: Two-group randomized controlled trial (RCT)

Sample Size: 30 participants are being sought for enrollment.

Study Duration: 12 months

Intervention Description: Home-based dual-task exercise training: combining aerobic exercise, balance training, strength, training, and simplified non-contact cardio kickboxing movements

Background and Significance:

Mild cognitive impairment (MCI) is an intermediate state between the cognitive decline expected with normal aging and more severe loss of cognition of Alzheimer's disease (AD) that effects more than 15% of older adults in the United States. MCI is associated with reduced attention, memory, physical functioning, as well as dualtask performance, and thus can be a significant burden to older adults.[1, 2] MCI also predicts AD with an annual conversion rate from MCI to AD equal to 15% in the United States.[3-5] Our rapidly aging society is ushering in a public health crisis for which we are not fully prepared. To better manage this approaching challenge and help preserve function and independence well into older age, we must develop and adopt innovative, evidence-based therapies that support cognitive and physical function in aging. Unfortunately, the COVID-19 pandemic has brought to the fore the need for effective and feasible therapies to help preserve function in the midst of the significant challenges posed by temporarily closed senior and recreation centers and the need for physical distancing that has isolated many older adults at home. Our team has demonstrated success in developing, implementing, and evaluating a community-based intervention to improve cognition and physical function in an older adult population.

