A total of 30 participants will be sought for enrollment, recruited from senior living communities, recreation centers, and other areas in which older adults congregate, via flyers and informational sessions. Once enrolled, participants will be randomly assigned to either control or intervention group. Baseline

measures will be completed among all participants prior to initiation of any intervention activities. At baseline physical function will be assessed using the Four-Stage Balance Test, the 30-Second Sit to Stand Test, and aerobic fitness will be assessed using the Six-Minute Walk Test. Cognitive function will be assessed using the Stroop Color-Word Test and Trail-Making Test A and B.

For participants in the intervention group, a 12-week home-based program will be delivered by computer tablet within each participant's home. Each participant will be loaned a tablet and stand and small exercise equipment (resistance bands, light dumbbells, and a body-bar). Two exercise sessions will be completed weekly on non-consecutive days for the duration of the program. To access videos, participants will log in to a password protected Vimeo site. For participants in the control group, no changes to current exercise habits will be made for the duration of the 12-week program. Upon completion of the 12 weeks, all participants will complete endpoint assessments that will be identical to the baseline assessments (physical and cognitive functions).

Study Participants

Inclusion Criteria: 1) male or female, 2) mild cognitive impairment with a score on the Montreal Cognitive Assessment 23 - 26 points, 3) > 65 years of age, 4) healthy enough for home-based physical activity as screened using the Physical Activity Readiness Scale for Older Adults.

Exclusion Criteria: 1) Having any condition that prevents safe participation in the physical activity component as screened using the Physical Activity Readiness Questionnaire for Older Adults; 2) likelihood of 4 withdrawing due to presence of severe illness; 4) having any amputation; 5) inability to provide informed consent, 6) Having a score of less than 15 points on the UBACC. Importantly, in reviewing and signing the consent form, the participant's score on the UBACC will be reviewed with the participant and ability to consent will be discussed to ensure the participant understands that they possess the ability to consent.

Informed Consent Process

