
Intervention: Participants receive two non-consecutive days per week of guided dual-task exercise. Sessions are 40 minutes in length with warm-up and cool-down.

Outcomes Measurement

Primary Objective

The main purpose of conducting this study is to assess the therapeutic benefits of a home-based dual-task exercise intervention on functional capacity in older adults, aged 65 years or older with mild cognitive impairment. To do so, a 12-week dual-task exercise program will be delivered via pre-recorded videos accessed by tablet computer. Baseline and endpoint assessment of physical function (balance, walking, and lower-body strength) will be conducted to compare changes in function between intervention and control participants.

Functional Capacity Measures

- Change in performance on the Four-Stage Balance Test (baseline to end point)

A Modified Four-Stage Balance Test is a literature-validated assessment of fall risk. It is based on the person's ability to hold four progressively more difficult stances for a duration of 10 seconds: side-by-side, tandem, left leg, and right leg. This test will be administered at baseline and end point.

- Change in performance on the Six-Minute Walk Test (baseline to end point)

The Six-Minute Walk Test will be used to assess changes in walking speed from baseline to end point. This assessment is a literature-validated test of physical function in older adults. Scoring is based on distance covered in in six minutes. This test will be administered at baseline and end point.

Secondary Objectives

The secondary purpose of conducting this study is to assess the therapeutic benefits of a home-based dualtask exercise intervention on functional capacity in older adults, aged 65 years or older with mild cognitive impairment. To do so, a 12-week dual-task exercise program will be delivered via pre-recorded videos accessed by tablet computer. Baseline and endpoint assessment of cognitive function (task-switching, memory, interference inhibition, and attention) will be conducted to compare changes in function between intervention and control participants.

Cognitive Function Measures

- Change in performance on the Stroop Color-Word Test (baseline to endpoint)

The Stroop Color Word Test will be administered at baseline and end point to assess interference inhibition, task-switching, and attention. This assessment is valid among older adults with mild cognitive impairment.

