- Change in performance on the Trail-Making Test (baseline to end point)

The Trail-Making Test parts A and B will be administered at baseline and end point to measure attention and working memory. It is a valid test for older adults with mild cognitive impairment.

Study Schedule

Projected Start Date: 12/15/2021.

Intervention Duration: 12 weeks

Study Duration: (planning, recruitment, intervention): 12 months

Study End Date: 12/31/2022

Study Timeline

- 1) Planning and Content Development: 09/01/2021 11/15/2021
- 2) Recruitment and Enrollment: 09/01/2021 05//21/2022
- 3) Baseline Assessment: 06/15/2022 07/05/2022
- 4) Intervention: 07/10/2022 10/10/2022
- 5) End Point Assessment: 10/05/2022 10/20/2022

Statistical Analysis Plan

Due to limited sample size and in response to a non-normal distribution, the key measure central tendency (Median) will be assessed along with interquartile range. Differences between intervention and control in median change scores will then be assessed quantitatively.

Change in physical and cognitive measures between intervention and control will be assessed first with calculation of a change score between baseline and endpoint for each group (intervention and control). These change scores will then be compared statistically using a separate Mann-Whitney U test (Median with interquartile range) for each outcome. Due to the small sample size, the ability to make deeper comparisons is very limited.

Risk/Benefit:

Limited risks to participants are associated with participation in non-physician supervised physical activity programming. These are: falls, musculoskeletal injury including strained muscles or joints that are frequently temporary and resolve on their own. Other minor risks include lightheadedness, exercise induced fatigue and diaphoresis, which will resolve on their own upon termination of the exercise challenge. Serious cardiovascular risks include sudden cardiac death, myocardial infarction, and stroke during exercise. These risks often significantly impact the health of the participant and the impacts of which are not fully reversible. However, serious adverse effects of exercise participation are very rare.

From the American College of Sports Medicine: "Contemporary estimates of major cardiovascular

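### Balance scoring is not defined; if it is a count of stances held, the difference in median change is too coarse to be the only effect estimate

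*Combined protocol and SAP*

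**What the plan says.** The Statistical Analysis Plan cites the limited sample and a non-normal distribution, and says that "the key measure central tendency (Median) will be assessed along with interquartile range". The between-arm effect is then described in one sentence: "Differences between intervention and control in median change scores will then be assessed quantitatively". For inference, change scores are to be "compared statistically using a separate Mann-Whitney U test (Median with interquartile range) for each outcome". No other effect estimate and no confidence interval is planned.

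Under Outcomes Measurement, Functional Capacity Measures lists two measures for the primary objective: change in the Four-Stage Balance Test and change in the Six-Minute Walk Test. The walk test has a stated score, the distance covered. The balance test is described only by the person's "ability to hold four progressively more difficult stances for a duration of 10 seconds", followed by the names of the stances. Whether the score is the number of stances held, the seconds held, or something else is not stated.

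On size, the Study design/methodology section says "A total of 30 participants will be sought for enrollment" and that "participants will be randomly assigned to either control or intervention group". It gives no allocation ratio, and the document gives no dropout allowance, alpha or target effect.

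**The concern.** A difference in medians suits an outcome with many distinct values, such as walking distance. It suits a short count badly. If balance is the number of stances held, most changes over 12 weeks will be −1, 0 or +1. The median of such data is itself almost always −1, 0 or +1, and it moves only when about half of an arm moves. A benefit in a substantial minority of the intervention arm then leaves both medians at 0.

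The test is not the problem, because Mann-Whitney ranks every change. The problem is that the one planned effect estimate can be exactly zero beside a small p-value or, in a study of this size, beside a non-significant one, where it is easily taken as evidence of no effect. A pilot's effect estimates are what a later trial is likely to carry forward, and this is a measure listed under the primary objective.

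**Working it through.** The plan gives no effect size or power figure, so there is nothing of its own to reproduce.

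**Inputs**
- Total sample: 30 sought (Research Synopsis; Study design/methodology).
- Effect measure, test, and median with interquartile range: Statistical Analysis Plan.
- Assumptions not in the documents: 1:1 allocation with no dropout (15 per arm), two-sided alpha 0.05, a 0 to 4 stance count, single-stance changes, the gain rates, and 5% losing a stance in each arm unless stated otherwise.

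**Step 1: when the median moves.** With 15 people the median is the 8th ordered value. With 7 gaining and 8 unchanged it is 0; with 8 gaining and 7 unchanged it is 1. With 14 per arm, exactly 7 gaining gives (0 + 1)/2 = 0.5. The difference between arms also moves if more than half of the controls decline.

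**Step 2: how often the medians are equal.** For true gain rate p, P(X ≥ 8) with X ~ Binomial(15, p) is 0.05 at 30%, 0.21 at 40%, 0.35 at 45%, 0.50 at 50% and 0.79 at 60%. With control gains at 10% and losses at 5%, the chance that the control median moves, or that either median falls, is negligible. So the chance of equal medians is close to 1 − P(X ≥ 8):

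| True gain rate, intervention v control | Medians equal |
|---|---|
| 30% v 10% | 95% |
| 40% v 10% | 79% |
| 50% v 10% | 50% |
| 60% v 10% | 21% |

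**Step 3: one worked result.** Suppose 7 of 15 gain a stance on intervention, 1 of 15 on control, and nobody declines.
- Median difference: 0 − 0 = 0.
- Mann-Whitney: U = 7×14 + 0.5×(7×1 + 8×14) = 98 + 59.5 = 157.5, against 15×15/2 = 112.5 under the null. With 22 zeros and 8 ones, the tie-corrected variance is (225/12) × [31 − ((22³ − 22) + (8³ − 8))/(30×29)] = 18.75 × (31 − 12.79) = 341.4, so the SD is 18.48. z = (45 − 0.5)/18.48 = 2.41, p = 0.016.
- Probability of superiority, P(intervention > control) + 0.5 P(tie) = 157.5/225 = 0.70.
- Difference in percentage gaining: (7 − 1)/15 = 40 percentage points.
- Hodges-Lehmann shift: of the 225 pairwise differences, 98 are +1, 119 are 0 and 8 are −1, so their median is 0. A median-type shift estimate has the same weakness.
- Interquartile ranges: 0 to 1 v 0 to 0.

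At 6/15 v 1/15, p = 0.036, the probability of superiority is 0.67 and the median difference is again 0.

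**Step 4: how often a zero effect sits beside p < 0.05.** At 40% v 10% with 5% losing a stance in each arm, the test is significant in about 37% of trials. It is significant with equal medians in about 20% of all trials (20 to 21% across repeat calculations; 23% without the continuity correction). The figure depends on the assumed losses:
- no losses in either arm: 28%;
- 5% losing on intervention and 20% on control: 34%;
- 40% gaining and 10% losing v 15% gaining and 15% losing: 14%.

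**Step 5: if balance is scored in seconds.** On a 0 to 40 second total, with an assumed shift of 3 s and SD of change of 5 s, the difference in medians is exactly 0 in under 1% of trials when times are kept to 0.1 s, and in about 7% when rounded to whole seconds.

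**The case against.** The strongest objection is that the five-level score is inferred. The description fits total seconds held as well as a pass/fail count, and in seconds the difficulty largely goes away. This stands: the point is conditional, and the documented gap is the missing scoring rule.

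A reader might infer that a real balance benefit would be reported as no benefit, or that the result could not be interpreted. The documents do not support either reading. The same section plans a Mann-Whitney test that uses every change, and it reports the interquartile range. At 40% v 10%, the upper quartile differs between arms in about 99% of the trials that are significant with equal medians, and in about 87% of all trials with equal medians. A typical line would be 0 (0 to 1) v 0 (0 to 0), p < 0.05, from which a careful reader would see that something moved. But an interquartile range is not a between-arm effect estimate, and none would be available to quote or to plan from.

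It is also fair that 15 per arm, the gain and loss rates, and the limit to single-stance changes have no source in the documents. The left-leg and right-leg stances could be gained together. The size of the problem varies widely over the range shown, so no single percentage should be read as a forecast.

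**Conclusion.** The point holds in conditional form. Balance scoring is undefined. If the score is a 0 to 4 count, the only planned effect estimate is insensitive to gains in fewer than about half of an arm: equal medians in 95% of trials at 30% v 10%, falling to 21% at 60% v 10%. A zero effect beside a significant test is then a realistic outcome, about one trial in five at 40% v 10% with 5% losses. The planned test is unaffected, and the interquartile range partly offsets the weakness, so this is a modest gap in how the effect is reported and not a flaw that invalidates the analysis.

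**What to change.** State how the Four-Stage Balance Test is scored.

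If it is a stance count, keep the Mann-Whitney test and the median with interquartile range. Add for balance the number and percentage in each arm gaining at least one stance and losing at least one. Give the between-arm difference in the percentage gaining, with a 95% confidence interval by a method suited to small counts, as the effect estimate. The probability of superiority with its interval is an alternative; it matches the test and keeps the information in multi-stance changes. Walking distance and the timed tests need no change on this account.

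If balance is scored in seconds, the addition is needed only if many participants are at the maximum at baseline.

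The cost is one or two sentences in the Statistical Analysis Plan and one extra table row, with no new data. The percentage gaining ignores the size of multi-stance changes, though the test still uses them. The Study Timeline puts endpoint assessment in October 2022, before this document's date, so if the results have already been seen the summary should be labelled as added.

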complications in exercise-based cardiac rehabilitation programs range from 1/100,000 to 1/300,000 participant exercise hours. Thus, exercise rehabilitation has been shown to be safe with serious events being rare. Moreover, the overall risk of a cardiac event appears to be reduced in persons who are regular exercisers".

There are no known direct benefits to participants in this study.

Data Safety Monitoring

Data safety monitoring will be conducted throughout this investigation by the PI. Weekly review and interim analyses of both safety and outcomes data will be conducted to monitor participant safety throughout the intervention. This will include both an ongoing quantitative review of adverse events and a qualitative assessment of participant experience in the intervention.

Adverse Event Reporting

Case report forms will be used for review and reporting of safety data. Prior to engaging in intervention activities, participants will be screened for safe physical activity participation using the PAR-Q for Older Adults. These data will be collected on an intervention data sheet and reviewed by the PD. Adverse events during the physical activity sessions will be recorded on the intervention data sheet for each participant and compiled into an Access Database.

Adverse event data collection will be performed monthly by direct contact with participants. Management strategies will be primary in pre-screening of participant risk via the Physical Activity Readiness Questionnaire for Older Adults. Non-serious adverse events that might occur include musculoskeletal pain, joint sprains / strains, lightheadedness, fatigue, shortness of breath, and overexertion. Serious adverse events include falls, syncope, sudden cardiac death, myocardial infarction, and cerebrovascular accident. Occurrence of a serious adverse event including hospitalization, myocardial infarction, sudden cardiac death, cerebrovascular accident, fracture, or death, that the PI determines might be research-related, will trigger an immediate suspension. In addition, any changes to the risk / benefit profile of the study determined by the literature, interim results, or other findings that indicate unexpected changes to the risks and potential benefits of the study will trigger a suspension. The PI reserves the right to suspend the research if any previously unforeseen event or problem presents risks to the participants.

References:

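### The investigator's safety review is weekly, but the only adverse event collection with a stated interval is monthly, and the home session sheet has no stated completer or return time

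*Combined protocol and SAP*

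**What the plan says.** **Review.** The Data Safety Monitoring section makes the PI responsible for monitoring: "Weekly review and interim analyses of both safety and outcomes data will be conducted to monitor participant safety throughout the intervention". It adds: "This will include both an ongoing quantitative review of adverse events and a qualitative assessment of participant experience in the intervention". It does not say what supplies either part, or when.

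**Collection.** The Adverse Event Reporting section gives two sources. One has an interval: "Adverse event data collection will be performed monthly by direct contact with participants". The other is a session record: "Adverse events during the physical activity sessions will be recorded on the intervention data sheet for each participant". Those records are compiled into a database, but nobody is named to complete the sheet and no return route or time is given.

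**Suspension.** The trigger is "Occurrence of a serious adverse event including hospitalization, myocardial infarction, sudden cardiac death, cerebrovascular accident, fracture, or death", qualified by "that the PI determines might be research-related, will trigger an immediate suspension".

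**Setting.** Under Study design/methodology and Intervention Description, the sessions are recorded videos followed on a tablet at home, twice a week for 12 weeks. They include balance, stepping and kickboxing movements. No staff attendance is described.

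**Falls and syncope.** Adverse Event Reporting states: "Serious adverse events include falls, syncope, sudden cardiac death, myocardial infarction, and cerebrovascular accident". The Risk/Benefit section puts falls among the limited risks: "These are: falls, musculoskeletal injury including strained muscles or joints that are frequently temporary and resolve on their own".

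**The concern.** The PI can judge only events that have been reported. A weekly review is therefore no more current than the data that reach it, and the one feed with a timetable is monthly. If nothing comes sooner, a fracture or hospitalization during a home session could reach the PI only at the next monthly contact, while the other participants go on with the same videos. After a fall or syncope without injury, the affected person could also carry on before anyone has looked at the event.

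The population adds to this. The Background section associates mild cognitive impairment with reduced attention and memory, so unprompted reporting, or recall over a month, is a weak safeguard. The protocol also states that participants have no known direct benefit, which makes avoidable exposure harder to justify. What is at stake is participant safety and the completeness of the safety data. The efficacy comparison is not affected.

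**Working it through.** The plan gives no figure for reporting delay, so there is none to reproduce. The check asks how much exercise fits between an event and the next scheduled contact.

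**Inputs from the protocol**
- 2 sessions a week for 12 weeks: 2 × 12 = 24 sessions per participant.
- Contact monthly; PI review weekly; 30 participants in total.

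**Assumptions**
- A month is 4 weeks.
- The intervention arm has 15 participants (the allocation ratio is not stated; range 10 to 20), all exercising concurrently.
- Adherence is 100% (range 50% to 100%).
- No sheet, call or family report arrives before the scheduled contact.
- For averages, event times are uniform between contacts.

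**Step 1: reviews against contacts.** 12 weeks hold 12 weekly reviews and 12 / 4 = 3 monthly contacts. So 12 − 3 = 9 reviews have no new contact-based data.

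**Step 2: sessions per continuing participant.** Maximum = sessions per week × interval in weeks; mean = half of that.

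| Collection | Maximum | Mean |
|---|---|---|
| Every 4 weeks | 2 × 4 = 8; 8/24 = 33% | 4; 4/24 = 17% |
| Weekly | 2 × 1 = 2; 2/24 = 8% | 1; 1/24 = 4% |

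With a 31-day month the maximum is 31/7 × 2 = 8.9, so 4 weeks does not inflate the result.

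**Step 3: sessions across the arm.** Maximum = arm size × maximum per participant.

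| Arm size | Every 4 weeks, full adherence | Every 4 weeks, 50% adherence | Weekly, full adherence |
|---|---|---|---|
| 10 | 80 of 240 | 40 | 20 |
| 15 | 120 of 360 | 60 | 30 |
| 20 | 160 of 480 | 80 | 40 |

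If the affected participant has stopped, 14 × 8 = 112 sessions remain in an arm of 15. The mean for that arm is 15 × 4 = 60 of 360.

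**Step 4: cost of weekly contact in both arms.** Extra contacts = 30 × (12 − 3) = 270. At an assumed 5 minutes each, 270 × 5 / 60 = 22.5 hours; at 10 minutes, 45 hours.

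**The case against.** **Immediate against monthly.** A reader might infer that the plan contradicts itself. It does not. Suspension is immediate once the PI has made a determination; it does not run from the moment of the event. The gap lies in how an event reaches the PI, not in the suspension rule.

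**Session sheets may already feed the weekly review.** This is a natural reading, with monthly contact as a backstop, and nothing shows that news does arrive only monthly. But the plan does not say that the sheets come back weekly or who completes them, so following it as written does not secure prompt notice.

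**The consent form.** A reader might infer that participants have no instruction to call. The documents do not support that. The consent form is not in the material available for review, and the protocol says it sets out what is expected of participants. A call-in rule may be there.

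**Falls and syncope.** A reader might infer that these fall outside the suspension trigger because its list names neither. But the list opens with a word that makes it illustrative, and the preceding text classes both as serious. On a plain reading both are covered if the PI thinks them possibly research-related. Only a minor clarification remains, because the Risk/Benefit wording sounds milder.

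**Worst cases.** The 120 sessions stack several worst-case conditions, and sessions done by others are exposure, not harm. Someone with a fracture, stroke or infarction would probably stop exercising. The protocol quotes 1/100,000 to 1/300,000 participant exercise hours for major cardiovascular complications. At 40 minutes a session, 120 sessions are 80 hours, or about 0.0003 to 0.0008 expected events. That rate comes from cardiac rehabilitation and does not cover falls or fractures, but it shows that the cardiovascular part is small. This objection stands as a limit on the size of the concern.

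**Unequal ascertainment.** Weekly collection in the intervention arm alone would make adverse event counts incomparable between arms. This stands, and the remedy must cover both arms.

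**Conclusion.** The concern holds as a procedural gap. The stated monthly interval does not match the weekly review, and the plan as supplied secures no faster route from a home session to the PI. If nothing arrives sooner, a trigger event could be learned of up to about 4 weeks late. In that time up to 8 of 24 sessions (33%) per continuing participant could take place, and at most 120 of 360 in an assumed arm of 15 at full adherence. The arm maximum runs from 40 to 160 over arm sizes of 10 to 20 and adherence of 50% to 100%. These are conditional upper bounds. They give no probability of a serious event, of harm or of a suspension.

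The change is worth making because it is concrete and cheap. Confidence is medium: the consent form could already close part of the gap. The planned intervention ran from 07/10/2022 to 10/10/2022 and the document is dated 02/07/2024, so the change helps only participants still to be treated.

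**What to change.** 1. **Replace monthly with weekly collection, by the same method in both arms.** Suggested text: 'Adverse events will be collected weekly from all participants, before the PI's weekly review, by a short returned form or a short call. Intervention participants will also complete the session data sheet after each session and return it weekly.' Because the session sheet exists in one arm only, base between-arm counts on the weekly collection common to both.
2. **Add a same-day report and a pause.** Suggested text: 'The participant or a family member will telephone study staff the same day after any fall, syncope, injury needing medical care, or hospitalization, and the participant will do no further session until the PI has reviewed it.' If the consent form already says this, repeat it here.
3. **Minor clarification.** Make the Risk/Benefit wording on falls agree with the serious-event list, and say outright that falls and syncope fall within the trigger, if that is the intention.

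**Cost.** A protocol amendment. Weekly telephone contact in both arms adds 270 contacts, or 22.5 to 45 staff hours at the assumed 5 to 10 minutes each; returned forms need less. A pause costs the participant a short loss of exercise and takes some PI time.

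If treatment is complete, report for each event its date, the date on which the PI learned of it, and the source: sheet, call or monthly contact.
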